## 9.6. Efficacy Analysis

### 9.6.1. Primary Efficacy Analysis

The efficacy analysis will be performed on the ITT population. The primary efficacy analysis will be performed based on 24 weeks of data after all subjects have completed the double-blind 24-week treatment period phase or discontinued before reaching 24 weeks of double-blind treatment (for this study one month equal to 4 weeks is considered). A higher response rate in the luspatercept over placebo and a p-value < 0.05 will confirm the superiority of luspatercept in the efficacy.

The primary efficacy endpoint of this study is defined as subjects with  $\geq 33\%$  reduction from baseline in RBC transfusion burden with a reduction of at least 2 units from Week 13 to Week 24 compared to the 12-week interval prior to randomization for luspatercept plus BSC versus placebo plus BSC.

For the early discontinued subjects, ie, who did not complete 24 weeks of double-blinded treatment period, the transfusion records will still be collected up to 48 weeks. All the transfusion records will be used to evaluate primary and secondary endpoints.

The first day to be used for statistical analysis will be defined as the date of the first dose. A transfusion received on Dose 1 Day 1 will be counted in the baseline transfusion burden.

The primary endpoint response rate is calculated using the number of responders divided by all subjects in the ITT population. The response rates of the subjects who randomized to luspatercept and the placebo will be calculated. Let  $P_1$  denote the true response rate in the luspatercept group, and  $P_2$  denote the true response rate in the placebo group. In the primary efficacy analysis, the statistical hypothesis is

$$H_0 : P_1 = P_2$$

$$H_a : P_1 \neq P_2$$

The number and percentage of subjects in the ITT population who achieve the response will be calculated for luspatercept and placebo. The difference in proportions between luspatercept and placebo will be calculated and the Cochran Mantel-Haenszel (CMH) chi-square test would be performed using randomization factors as strata, corresponding 95% confidence interval (CI)

associated with the test will be provided. A higher response rate in the luspatercept arm over placebo arm with a p-value < 0.05 will infer that luspatercept is significantly superior to placebo.

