4.3 Stratification, Randomization, and Blinding

Subjects were randomized to receive luspatercept or placebo at a 2:1 ratio. Randomization was accomplished by an IVRS/IWRS to ensure timely registration and randomization. A stratified randomization schedule was implemented. Randomization was stratified by the following geographical regions:

- North America and Europe (including Bulgaria, Canada, France, Greece, Italy, United Kingdom and United States)
- Middle East and North Africa (including Israel, Lebanon, Tunisia and Turkey)
- Asia-Pacific (including Australia, Malaysia, Taiwan and Thailand)

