5. GENERAL STATISTICAL CONSIDERATIONS

5.1 Reporting Conventions

Summary tables, listings, figures and any supportive SAS outputs will include a “footer” of explanatory notes that will indicate, at a minimum, the following:

- Program source (e.g., SAS program name, including the path, that generates the output) and
- Data extraction date (e.g., the data cutoff date, database lock date, run date).

The purpose of the data extraction date is to link the output to a final database, either active or archived, that is write-protected for replication and future reference. An output date will also appear on each output page and will indicate the date the output was generated by the analysis program.

The following reporting conventions apply generally to tables, listings, and figures:

- Data from all study centers will be combined for analysis;
- All stratified efficacy analyses will use randomization factor as stratum;
- All statistical tests of the treatment effect will preserve a significance level of 0.050 for 2-sided tests. Testing of interactions will be performed at the 0.100 significance level, unless specified otherwise;
- P-values will be rounded to 4 decimal places. P-values that round to 0.0000 will be presented as ‘<0.0001’ and p-values that round to 1.000 will be presented as ‘>0.9999’;
- Confidence intervals (CIs) will be presented as 2-sided 95% CIs unless specified differently in specific analysis;
- Summary statistics will consist of the number and percentage of subjects (or cycles, if appropriate) in each category for discrete variables, and the sample size, mean, median, Standard Deviation (SD), Q1, Q3, minimum, and maximum for continuous variables;
- All mean, median, Q1, and Q3 values will be formatted to one more decimal place than the measured value. Standard deviation values will be formatted to two more decimal places than the measured value; Minimum and maximum values will be presented to the same number of decimal places as the measured value.
- All percentages will be rounded to one decimal place. The number and percentage of responses will be presented in the form XX (XX.X%), where the percentage is in the parentheses; when

the number of a response is zero, percentage will not be presented for that response;

- All listings will be sorted for presentation in order of treatment group, study center, subject, and date of procedure or event if not otherwise specified.

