10.2 Completed Analysis of Primary Efficacy Endpoint

The primary endpoint response rate is defined as the number of responders (subjects who achieve an erythroid response during the 12-week interval from Week 13 to Week 24 compared to baseline) divided by the number of subjects in the ITT population within each treatment group. The

erythroid response is defined as subjects with $\geq 33\%$ reduction from baseline in RBC transfusion burden with a reduction of at least 2 units, where the 12-week interval on or prior to Dose 1 Day 1 is used as baseline value. Specifically, if a subject is not treated, the 12-week interval on or prior to randomization date will be used as baseline value.

The 12-week RBC transfusion burden (units/12 weeks) is calculated as Number of RBC units transfused during the 12-week interval.

The following statistical hypothesis was tested:

$H_0: P_1$ (response rate in the luspatercept group) = P_2 (response rate in the placebo group)

$H_a: P_1 \neq P_2$

The treatment comparison (luspatercept plus BSC versus placebo plus BSC) was conducted by the Cochran Mantel-Haenszel (CMH) test stratified by the geographical regions defined at randomization as stratification factor. The odds ratio (OR) (luspatercept versus placebo) with corresponding 2-sided (at 0.05 alpha level) 95% CI and p-value was provided.

The number and percentage of responders were summarized by each treatment group and the difference in proportions (luspatercept – placebo) and corresponding 95% CI were also calculated by unconditional test.

A forest plot showing the ORs, 95% CI and p-value for the overall result and the results in each subgroup was constructed.

Listing of individual RBC transfusion data was provided.

No further analysis for the primary efficacy endpoints will be included in the final CSR.

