10.5.1 The Transfusion Reduction based on the Rolling Method

To measure the duration of transfusion burden reduction, time to the first erythroid response, transfusion independence and duration of transfusion independence, rolling method will be applied. The summary based on rolling method intends to reflect consistency with clinical practice. Please refer to Sections 10.5.7, 10.5.8, and 10.5.9 for more details.

The transfusion reduction will be measured using the consecutive “rolling” 12-week (or 24-week) time interval within the entire study period up to the efficacy cutoff, i.e., Days 2 to 85, Day 3 to 86 (or Day 2 to 169, Day 3 to 170 for 24-week) and so on. Note that, day 1 transfusion belongs to baseline. The transfusion reduction by 12-week is defined as subjects with $\geq 33\%$ (or 50%) reduction from baseline in RBC transfusion burden with a reduction of at least 2 units. The

transfusion reduction by 24-week is defined as subjects with $\geq 33\%$ (or 50%) reduction from baseline in RBC transfusion burden only (i.e., without considering the absolute unit reduction).

The treatment comparison with “rolling” method (luspatercept plus BSC versus placebo plus BSC) will be conducted by the CMH test stratified by the geographical regions defined at randomization as stratification factor. The OR (luspatercept versus placebo) with corresponding 2-sided (at 0.05 alpha level) 95% CI and p-value will be provided. The number and percentage of responders will be summarized by each treatment group and the difference in proportions (luspatercept – placebo) and corresponding 95% CI will also be calculated by exact unconditional test with “rolling” method as well.

A forest plot showing the ORs, 95% CI and p-value for the erythroid response (33% and 50%) in each subgroup will be provided with “rolling” method (by 12-week or 24-week respectively) as well.

A waterfall plot will be provided for the transfusion burden percent change from baseline during any 12-week or 24-week interval by treatment group respectively. Individual subject’s transfusion burden percent change from baseline will be displayed in a single bar. The displayed transfusion burden percent change is each subject’s largest percent decrease in transfusion burden during any post-baseline 12-week or 24-week interval.

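### For the rolling response endpoints, the interval for the difference in proportions is exact unconditional and takes no account of region, beside a CMH test stratified by region: valid but conservative, and easily supplemented

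*SAP*

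**What the plan says.** Region is the only stratification factor. In SAP 4.3, "Randomization was stratified by the following geographical regions", and three regions follow.

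In SAP 10.5.1 the treatment comparison for the rolling responses "will be conducted by the CMH test stratified by the geographical regions defined at randomization as stratification factor". Next, "The OR (luspatercept versus placebo) with corresponding 2-sided (at 0.05 alpha level) 95% CI and p-value will be provided". The difference between the responder percentages is then added, and its "corresponding 95% CI will also be calculated by exact unconditional test". No strata or regional weights are named for that interval. The section is in the future tense, which SAP section 2 reserves for analyses to be updated in the final CSR.

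SAP 10.2 describes the same pairing for the completed primary endpoint: "the difference in proportions (luspatercept – placebo) and corresponding 95% CI were also calculated by unconditional test", here without the word exact. It closes that analysis for the final CSR, and SAP 10.3 closes the key secondary ones.

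Protocol 9.6.1 plans the difference in proportions, a CMH test with the randomization factors as strata, and a 95% interval "associated with the test will be provided. A higher response rate in the luspatercept arm over placebo arm with a p-value < 0.05" is then the criterion for superiority. Protocol 9.6.3.10 promises an interval of the same kind for transfusion independence. SAP 10.5.9 keeps the stratified CMH model there but names no interval for the comparison.

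**The concern.** The absolute difference is the effect size that clinicians read first. Here its interval appears to come from the pooled two-by-two table, although randomization, the test and the ANCOVA and negative binomial models all use region. If response rates differ between regions, a pooled interval carries between-region variation that the stratified test removes. An exact unconditional interval is also conservative in its own right. A results table could then show a significant p-value beside a difference whose interval includes 0, with nothing to explain why.

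**Working it through.** **The plan's own figure.** SAP 4.4 assumes 40% against 20%, 2:1 allocation, 90% power, two-sided 0.05 and 10% drop-out. Placebo n without continuity correction = [1.96·√(0.2222×1.5) + 1.2816·√(0.16 + 0.24/2)]² / 0.2² = 81.9. With the correction, (81.9/4)·[1 + √(1 + 6/(81.9×2×0.2))]² = 89.2, rounded up to 90. Then 90 + 180 = 270, and 270/0.9 = 300. The figure reproduces; it supplies inputs here but does not bear on the point.

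**Is the interval unstratified?** The SAP does not use that word. An exact unconditional interval for a difference is a two-by-two method, and no stratified version is described. SAP 5.1 does not change this: "All stratified efficacy analyses will use randomization factor as stratum" fixes the stratum for analyses that are already stratified.

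**Width lost by ignoring region.** Assume three equal regions, 200:100 overall, 2:1 in each, and a 20-point difference in each. The pooled variance is U = p̄₀(1−p̄₀)/100 + p̄₁(1−p̄₁)/200. The stratified variance S uses the regional average of p(1−p) instead. The width ratio is √(U/S).

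| Assumed placebo rates | U | S | Ratio |
|---|---|---|---|
| 20/20/20% | 0.002800 | 0.002800 | 1.00 |
| 10/20/30% | 0.002800 | 0.002700 | 1.02 |
| 5/20/35% | 0.002800 | 0.002575 | 1.04 |
| 5/20/50% | 0.003113 | 0.002588 | 1.10 |

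Simulation (4,000 trials per scenario) gives mean widths of 0.205 v 0.199, 0.205 v 0.193 and 0.217 v 0.194 for the last three rows, that is 3%, 6% and 12%. It also gives about 1% when regions are alike, so a little of each simulated gap is a small-sample effect rather than region.

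**Width added by the exact method.** At the design's expected counts (80/200 v 20/100) the pooled Wald interval is 0.096 to 0.304, width 0.207. The exact unconditional interval uses 2.5% in each tail, maximised over the nuisance rate. It is 0.078 to 0.318 (16% wider) when tables are ordered by the raw difference and 0.079 to 0.300 (7% wider) when ordered by the score statistic. The SAP does not say which applies.

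**An illustrative table (assumed counts).** Luspatercept 14/80, 13/60, 22/60; placebo 2/40, 6/30, 6/30; pooled 49/200 v 14/100.

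- CMH: observed minus expected = 3.333 + 0.333 + 3.333 = 7.0. Variance = 3.107 + 3.368 + 4.335 = 10.81. Chi-square = 49/10.81 = 4.53, p = 0.033.
- Mantel-Haenszel odds ratio: 2.03 (1.05 to 3.94).
- Mantel-Haenszel risk difference, weights n₁n₀/N = 26.67, 20, 20: 7.0/66.67 = 0.105 (0.016 to 0.194, Sato variance).
- Pooled Wald: 0.105 ± 1.96·√(0.245×0.755/200 + 0.14×0.86/100) = 0.015 to 0.195.
- Exact unconditional, raw difference: −0.018 to 0.226. One-sided p at zero difference is 0.047 (raw) or 0.028 (score); both exceed 0.025, so either version includes 0.

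**How often the two disagree.** The table shows the share of simulated trials with CMH significant and the pooled analysis not, at regional sizes 80/60/60 v 40/30/30. The exact columns rest on 40,000 trials per scenario. The last column rests on 100,000 and uses a pooled large-sample score test, which isolates region.

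| Placebo rates, effect | Exact, raw | Exact, score | Pooled, not exact |
|---|---|---|---|
| 20% in all, 40% v 20% (design) | 2.2% | 2.5% | under 0.1% |
| 20% in all, OR 2 | 10.2% | 7.7% | 0.1% |
| 10/20/33%, OR 2 | 14.7% | 11.2% | 2.8% |
| 5/15/45%, OR 2 | 24.3% | 19.4% | 10.3% |

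The exact interval never excluded 0 when CMH was non-significant.

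**The case against.** Much of the case on the other side stands.

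- An interval in line with the p-value is already reported: the odds ratio's, given with the CMH test. A reader might infer that nothing in the table matches the test. The mismatch concerns only the difference.
- Protocol 9.6.1 governs the primary endpoint, and its interval could be read as the odds-ratio interval. The protocol's visible endpoint table does not list the rolling 33% and 50% responses. For them the departure is from the protocol's general approach, not from a specific commitment. For transfusion independence the commitment is explicit.
- A reader might blame the disagreement on region. In the illustrative table it is the exact method: the pooled Wald interval also excludes 0. Region becomes a large contributor only under the most extreme rates.
- Regional heterogeneity is assumed. The protocol cites a paper on geographical variation in transfusion practice, but response is measured against each subject's own baseline, so different practice need not mean different response.
- A Mantel-Haenszel interval with Sato variance does not invert CMH exactly. In the table its implied p is 0.021 against 0.033, and in simulation it excluded 0 with CMH non-significant in 3-4% of trials at OR 2 and under 1% at the design rates.
- The pooled difference equals the gap between the printed percentages; a weighted one need not.

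These points limit the size of the problem. They do not explain why the difference alone takes no account of region.

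**Conclusion.** The point holds as a minor reporting matter. The interval for the rolling-response difference is valid but wider than it needs to be, and it can include 0 beside a significant stratified test. Region contributes about 0% when regions are alike, 2-5% at moderate and 10-12% at extreme assumed differences; the exact method contributes the rest. The conclusion depends on reading the interval as pooled, which the method named implies but the SAP does not state.

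A reader might go further and infer that the primary result or the error rate is in doubt. The documents do not support that. Superiority rested on the CMH p-value, the rolling endpoints lie outside the hierarchical testing sequence, and the interval errs only on the conservative side. Nor is there a case for redoing the completed primary and key secondary analyses. It is enough to note that the primary endpoint's interval for the difference, by the method SAP 10.2 names, is unstratified.

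**What to change.** For the rolling endpoints in the final CSR, make a region-stratified risk difference with its 95% interval the main interval for the difference, by stratified Miettinen-Nurminen or Mantel-Haenszel. Keep the exact unconditional interval as supportive, label it unstratified, and state its ordering statistic. Do the same for transfusion independence, so that SAP 10.5.9 delivers the interval promised in Protocol 9.6.3.10. Add one line noting that the primary endpoint's interval is unstratified, with no re-analysis.

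Of the two, stratified Miettinen-Nurminen with weights n₁n₀/N aligns better with the test. At zero difference its variance per region is (n₁n₀/N)²·[m(N−m)/N²]·[N/(n₁n₀)]·[N/(N−1)] = n₁n₀m(N−m)/[N²(N−1)], where m is the number of responders. This is the CMH variance, so the two agree on whether 0 is excluded.

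The cost is a small programming change and no new data. The drawbacks are that the weighted difference may differ slightly from the raw one, which a footnote can explain, and that a Mantel-Haenszel interval, if chosen, agrees closely but not exactly with the CMH p-value.

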10.5.2 Mean Change in Liver Iron Concentration

Quality Control for LIC measurements: An imaging charter (MRI Manual) was distributed to all participating sites to specify appropriate MRI imaging parameters and scanning techniques. All sites were required to submit one dummy MRI LIC assessment file for review of the imaging parameters prior to enrolling subjects into the study. Dummy scans were reviewed by an independent expert. Feedback was provided back to the sites if dummy scan review highlighted non-compliance with MRI manual. Following the baseline and 24-week visits, random and for-cause spot checks of source DICOM images were performed. Independent analysis of the LIC values was performed using techniques validated against MRI LIC acquisition (Wood et al, 2005). The sponsor was informed of the independent audit results.

The value of LIC will be either the value collected from eCRF or the value derived from T2*, R2* or R2 parameter depending on which techniques and software were used for MRI LIC acquisition and post-processing. The LIC value will be derived as below:

Technique	Site number	Derivation source	Alternative derivation if still missing
Ferriscan R2		Reported LIC from CRF	$(29.75 - \text{SQRT}(900.7 - 2.283 * \text{EXP}((-0.19043 + 1.016385 * \ln(R2)) / 0.983615)))^{1.4265}$.

T2*/R2*	[REDACTED]	$31.94 * (T2*)^{-1.014}$	$0.029*(R2*)^{1.014}$ If both T2* and R2* are missing, LIC from CRF will be used
		$25.4/T2* + 0.2$	$0.0254 * (R2*) + 0.2$ if site is not [REDACTED]. If both T2* and R2* are missing, LIC from CRF will be used.
		$0.0254 * (R2*) + 0.2$	$25.4/T2* + 0.2$ If both R2* and T2* are missing, LIC from CRF will be used

The derived LIC value will be used for analysis. If a subject has any LIC value > 43, the subject’s LIC value will be excluded from analysis. Note that, subjects with LIC value > 43 are not excluded from the LIC baseline summary and efficacy subgroup analysis by LIC categories.

In the primary CSR, descriptive statistics for LIC measurements and change from baseline were summarized at week 24/48. The 24/48-week LIC change from baseline was analyzed using ANCOVA model with geographical regions defined at randomization and baseline LIC as covariates for the ITT population. Additionally, a shift table representing the shift from the baseline to week 24/48 category (≤ 3 ; $> 3-\leq 7$; $> 7-\leq 15$ and > 15) was provided for LIC. A subject has maximum two post-baseline LIC assessments (including “unscheduled”) during the 48-week double-blinded treatment period per protocol. If a subject has only one assessment, it is counted as “Week 48” visit; if a subject has two assessments, the first one is counted as “Week 24” visit, and the later one as “Week 48” visit regardless of the collected nominal visit name. This logic was used in the model based summary, change from baseline summary and the shift table summary for the primary CSR.

For the final CSR, descriptive statistics for LIC measurements and change from baseline will be summarized at weeks 24, 48, 96, 144, and 192. The 24/48/96-week LIC change from baseline will be analyzed using ANCOVA model with geographical regions defined at randomization and baseline LIC as covariates for the ITT population. Additionally, a shift table representing the shift from the baseline to week 24/48/96/144/192 category (≤ 3 ; $> 3-\leq 7$; $> 7-\leq 15$ and > 15) will be

provided for LIC. Post-baseline is defined as the closest visit at Weeks 24, 48, 96, 144 or 192 if the assessment is on or before the efficacy cutoff. If the assessment occurs after the efficacy cutoff, the assessment is not included in the reported visit. The efficacy cutoff is defined as min (death date, study discontinuation date, last dose date + 20). Only Weeks 24, 48 and 96 are analyzed for Placebo. This logic will be used in the summary, change from baseline summary and the shift table summary for the final CSR.

Additionally, bar plot was provided for baseline, week 24 and week 48 LIC categories (≤ 3 ; $>3-\leq 7$; $>7-\leq 15$; >15). Percent of subjects within each category were displayed by treatment group. No bar plots will be provided in the final CSR.

All the LIC data will be presented in a listing.

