-  Day 22 post-last dose corresponds to the end of Treatment Period.
-  Calculated doses requiring reconstituted volume greater than 1 mL should be divided equally into two syringes and injected into two separate sites – same anatomical location but opposite side of the body (example left thigh and right thigh). In case of 2 simultaneous injections, the injection sites must be different. In case of dose delays refer to Section 6.2.1 and Section 6.3.1. Only for Dose 1 Day 1, IP administration should be at the end of the Screening/Run-in period, which is at least 12 weeks.
-  Assessments to be performed if the subject is in this study at Week 96, not applicable if subject does not enter into the LTTP.
-  During the Long-term Treatment Period, PK and ADA samples will be collected every 6 doses. The maximum ADA monitoring period will be two years from dose 1 day 1 of the double-blind Treatment Period. During the Open-label Phase: for placebo-cross-over subjects, if positive at unblinding, continue every 6 doses up to 2 years from Dose 1 Day 1 of the double-blind Treatment Period; for subjects continuing treatment with luspatercept, only if positive at unblinding, every 6 doses up to 2 years from Dose 1 Day 1 of the double blinded treatment period. During the Post-Treatment Follow-Up : Before unblinding, ADA monitoring, every 24 weeks (post last dose), at post-treatment follow-up visits will continue for up to two years from Dose 1 Day 1 of the double-blind Treatment Period. After unblinding, ADA monitoring, every 24 weeks (post last dose), at all post-treatment follow-up visits will continue only if subjects' last available ADA is positive and have not reached the 2-year maximum limit for ADA monitoring. ADA/PK sampling per Investigator's or Sponsor's discretion is allowed and should be recorded as unscheduled visit.
-  During the Long-term Treatment Period these parameters should be measured by Central Lab. Data to be entered in the eCRF.
-  MRI for LIC, myocardial iron (T2\*) and for spleen volume can be performed on one MRI acquisition if possible.

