**All subjects**, ie, subjects who are continuing the treatment with luspatercept after the unblinding of the study, and subjects who are starting the treatment with luspatercept after received placebo in the double-blind treatment, will perform the following assessments and procedures:

- Iron chelating therapies: record on an ongoing basis (as detailed in [Section 6.1](#)).
- Concomitant medications/therapies: such as surgery, radiation, systemic or any other therapy for the subject's disease - record on ongoing basis.
- Concomitant procedures - record on ongoing basis.
- Transfusion assessment - record on an ongoing basis (as detailed in [Section 6.1](#)). In addition, as detailed in [Section 6.1](#), a subject diary will be available (refer to [Section 6.1](#))
- Adverse event assessment - record on an ongoing basis as detailed in [Section 6.1](#) and [Section 10](#).
- Malignancy and Pre-Malignancy Reporting (refer to [Section 6.1](#) and [Section 10.5.2](#) for additional information)
- Vital signs (as detailed in [Section 6.1](#))
- Weight
- Female subjects of childbearing potential: Urine or serum medically supervised pregnancy test with a minimum sensitivity of 25 mIU/mL for FCBP at Day 1 of each dose
- Female subjects of childbearing potential: menstrual status
- Hematology (as detailed in [Section 6.1](#))
- ADA (if applicable) – refer to [Section 6.9](#) and [Table 3](#)

- HRU
- Administration of luspatercept on Day 1 of each dose
- Only at Week 96 post first dose, if applicable, ie, for subjects who entered Open-label Phase prior to reaching Week 96 in the Long-term Treatment Period:
  - MRI for LIC (mg/g dw) (as detailed in Section 6.1) - only at week 96 post first dose, if applicable.
  - MRI for myocardial iron (T2\*; ms) - only at week 96 post first dose, if applicable.
  - MRI or abdominal ultrasound for spleen measurement (as detailed in Section 6.1) - only at week 96 post first dose, if applicable.
  - Bone imaging DXA scan (as detailed in Section 6.1) - only at week 96 post first dose, if applicable.

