10.5.4 Mean Change in Serum Ferritin Level

In the primary CSR, descriptive statistics for serum ferritin level have been summarized at baseline and the post-baseline visit, where the baseline mean serum ferritin was measured during the 12 weeks prior to the first dose and the post-baseline mean serum ferritin was calculated during the last 12 weeks of the 48- week double-blind treatment period or the last 12 weeks of the study treatment for early discontinued subjects. Change from baseline has been summarized at the post-baseline visit.

For the final CSR, the post-baseline will be calculated as the mean of serum ferritin values during the last 24 weeks on or prior to Week 48, Week 96, Week 144 , Week 192, *etc.* if the assessments are on or before the efficacy cutoff date. If the assessments occur after the efficacy cutoff, the assessments will not be included in the reported interval. The overall post-baseline serum ferritin calculated by the mean of last 24-week serum ferritin prior to the efficacy cutoff date will also be conducted. The definition of baseline mean serum ferritin remains the same as in the primary CSR. The descriptive statistics will be summarized at each post-baseline time point.

The change from baseline in serum ferritin at the Week 48, Week 96, and overall post-baselines will be analyzed using an ANCOVA model with the geographical regions defined at randomization and baseline serum ferritin value as covariates for the ITT population.

All the serum ferritin data will be presented in a listing.

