10.5.5 Bone Mineral Density Assessed by DXA Scan

In the primary CSR, a subject has only one post-baseline DXA assessment during the 48-week double-blinded treatment period per protocol amendment 1. The only post-baseline assessment is counted as “week 48” visit regardless of the collected nominal visit name. For patients enrolled before protocol amendment 1, there would be maximum 2 DXA assessments during the 48-week double-blinded treatment period. In this case, if a subject has only one assessment, it is counted as “Week 48” visit; if a subject has two assessments, the first one is counted as “Week 24” visit, and the later one as “Week 48” visit regardless of the collected nominal visit name. The analysis has been done on subjects that have at least two measurements (one baseline and one post-baseline measurement).

For the final CSR, post-baseline is defined as the closest visit at Week 48, Week 96, Week 144 or Week 192 if the assessment is on or prior to the efficacy cutoff. If the assessment occurs after the efficacy cutoff, the assessment will not be included in the reported visit.

Descriptive statistics for BMD and T-score baseline, post- baseline, and change from baseline will be summarized for Week 48/96/144/192 visit. Change from baseline at Week 48/96 will be

analyzed using ANCOVA model with the geographical regions defined at randomization and baseline measurement as covariates for the ITT population.

All the DXA data will be presented in a listing.

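### The final-CSR imaging summaries at Weeks 144 and 192 have no scheduled on-treatment scans behind them, and the last dose + 20 cutoff excludes the nominal Day 22 end-of-treatment scan

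*SAP*

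**What the plan says.** **Planned outputs.** For LIC, "descriptive statistics for LIC measurements and change from baseline will be summarized at weeks 24, 48, 96, 144, and 192" (SAP 10.5.2), with a shift table at the same weeks; placebo LIC stops at Week 96. For DXA, "post-baseline is defined as the closest visit at Week 48, Week 96, Week 144 or Week 192" (SAP 10.5.5). SAP 10.5.6 uses the same rule for myocardial iron and adds a T2* shift table. The ANCOVAs cover Weeks 24, 48 and 96 for LIC, and Weeks 48 and 96 for DXA and T2*. For ferritin, "the post-baseline will be calculated as the mean of serum ferritin values during the last 24 weeks on or prior to Week 48", and likewise for Weeks 96, 144 and 192 (SAP 10.5.4). An overall value over each subject's last 24 weeks before cutoff is also planned. Ferritin ANCOVAs are at Week 48, Week 96 and overall.

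**Cutoff.** "The efficacy cutoff is defined as min (death date, study discontinuation date, last dose date + 20" days (SAP 10.5.2), and "If the assessment occurs after the efficacy cutoff, the assessment is not included in the reported visit". SAP 10.5.5 and 10.5.6 repeat the exclusion.

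**Protocol schedule.** Table 3 gives Week 96 as the last on-treatment time point for LIC, T2* and DXA. Section 6.4 says the same for the Open-label Phase: "Only at Week 96 post first dose, if applicable". After that, Table 3 asks for a scan in the Day 22 Post Last Dose / Treatment D/C column, if none was done in the previous 12 weeks (24 for DXA). Footnote 7 reads "Day 22 post-last dose corresponds to the end of Treatment Period". The Week 144 visit in post-treatment follow-up counts from the last dose and carries no imaging.

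**The concern.** A table column headed Week 144 or Week 192 implies a planned assessment at that time, and here there is none. The one protocol scan that could supply a later on-treatment value is set for a day just past the cutoff. Columns would then be filled from whatever scans happen to lie before it. SAP 10.5.2, 10.5.5 and 10.5.6 assign scans to the closest time point without giving a window width, so a scan far from the named week can carry its label. The same cutoff also bears on Week 48, where a treatment comparison is made: part of the permitted scan window lies beyond it for subjects who stop after Dose 16. SAP 10.5.2 describes how scans were assigned to visits in the primary CSR without mentioning such a cutoff, so the Week 48 figures in the two reports could differ.

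**Working it through.** **1. Day grid.** SAP 5.1 ends Weeks 24, 48, 96, 144 and 192 on Days 169, 337, 673, 1009 and 1345. The formula 7w + 1 reproduces all five (for example 7 × 48 + 1 = 337). That grid is written for transfusion endpoints. Protocol 3.1.2 counts the 48 weeks from Study Day 1, which gives 48 × 7 = Day 336. Both counts are carried below.

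**2. End-of-treatment scan against the cutoff.** Day 22 post last dose is last dose + 21 if the dosing day is Day 1, otherwise + 22. The cutoff is + 20, so the nominal scan is 21 − 20 = 1 or 22 − 20 = 2 days late. Protocol 6.5 places the visit within 22 days of the last dose, so a scan on days 0 to 20 is kept. It also allows a later visit when the decision to stop comes more than 22 days after the last dose, and such a scan is dropped too.

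**3. Whether that scan would be due at Week 144 or 192.** The last scheduled scan is at Week 96, which is 144 − 96 = 48 or 192 − 96 = 96 weeks earlier. The 12-week (MRI) and 24-week (DXA) exemptions would not apply unless an unscheduled scan had been done.

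**4. What the labels can absorb.** If closest means nearest in time, the boundaries are (96 + 144)/2 = Week 120 and (144 + 192)/2 = Week 168. Any scan between Weeks 120 and 168 becomes Week 144, and any later scan becomes Week 192.

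**5. Week 48 scan window.** Dose k on schedule is Day 1 + 21(k − 1); cutoff is dose day + 20; Table 3 footnote 17 allows ±10 days.

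| Last dose | Dose day | Cutoff | Days kept, Week 48 = Day 337 (327–347) | Days kept, Week 48 = Day 336 (326–346) |
|---|---|---|---|---|
| 15 | 295 | 315 | 0 of 21 | 0 of 21 |
| 16 | 316 | 336 | 10 of 21 | 11 of 21 |
| 17 | 337 | 357 | 21 of 21 | 21 of 21 |

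After Dose 16 the scan on the nominal day is lost by one day on the Day 337 count and kept on the Day 336 count. Week 96 behaves alike: on the Day 673 count, last doses 31, 32 and 33 keep 0, 10 and 21 of 21 days.

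**6. Ferritin.** Table 3 requires it every 4 doses in the Long-term Treatment Period and at Day 22, but shows a dash at open-label Dose X. The list for all subjects in Section 6.4 omits it. The row label nevertheless says to use local laboratories in the Open-label Phase. SAP 11.4.2 calls ferritin a central-laboratory measure, while SAP 11.4 says all open-label laboratory data are local.

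As an assumption, take the earliest first dose as 25 August 2015 plus 12 weeks, which is 17 November 2015. The span to 11 May 2018 is then 906 days, or about 129 weeks. Scheduled long-term-period samples could therefore reach only the start of the Week 144 window (Weeks 120–144) for the earliest subjects, and not the Week 192 window (Weeks 168–192).

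**The case against.** The cutoff is a coherent on-treatment rule. It matches the treatment end date in SAP 9.1, the general efficacy cutoff in SAP Section 10 and the 21-day dosing interval. The Week 144/192 outputs are descriptive, tables show sample sizes, imaging data are listed, and none of these endpoints is in the gatekeeping sequence. All of that stands. It limits the consequences but does not supply scheduled data for Weeks 144 and 192, nor explain why a protocol-required end-of-treatment scan should miss by a day or two.

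Four stronger readings are tempting, and the documents do not support them:

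- *That no discontinuation scan survives.* Section 6.5 allows the visit earlier, and scans by day 20 are kept.
- *That the remaining late scans were done for clinical cause.* No passage gives a reason for them; routine care is equally possible. The for-cause checks in SAP 10.5.2 are audits of images.
- *That subjects stopping after Dose 16 lose their Week 48 scan.* This turns on Day 337 or Day 336, and visit windows and dose delays move the dates as well. Subjects who receive Dose 17 on schedule lose nothing.
- *That the overall ferritin ANCOVA has no data.* It uses each subject's own last 24 weeks before cutoff. Those stopping in the double-blind periods, and placebo subjects up to crossover, have scheduled samples there.

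**Conclusion.** The mismatch is real and confined to the final CSR. No on-treatment MRI or DXA is scheduled after Week 96, and the nominal Day 22 scan falls one or two days past the cutoff. For last dose = Dose 16 on schedule, 10 or 11 of the 21 Week 48 window days are kept. These results rest on on-schedule dosing and the nominal visit day. The number of scans affected, and the number of scans that exist near Weeks 144 and 192, cannot be told from the documents. Primary-CSR results are unaffected. The matter is worth correcting because the rule discards scans the protocol asks for and can label stray ones as planned visits.

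**What to change.** 1. For MRI and DXA, and for the Day 22 ferritin sample, count assessments recorded at the Day 22 / Treatment Discontinuation visit as on treatment. Set the cutoff at the later of last dose + 20 and that visit, still capped at death, study discontinuation and, for placebo, crossover.
2. Replace the Week 144 and Week 192 imaging columns, including the LIC and T2* shift tables, with the last on-treatment assessment and its study week.
3. State which day is Week 48 for imaging, since SAP 5.1 defines it only for transfusion endpoints.
4. Keep the overall ferritin ANCOVA. Reconcile the dash at open-label Dose X with the local-laboratory note and with the planned Week 144/192 ferritin means.

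The cost is one derived date and relabelled tables, with no new scans. The downside is that some values will fall a few days after the 21-day dosing interval, and more where the decision to stop came late; showing days since last dose would make this visible.

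The change does not restore off-drug Week 48 scans of subjects who stopped earlier. Table 3 schedules those scans, and Protocol 9.6.3.1 and 9.6.3.5 use the last earlier value when Week 48 is missing, whereas the final-CSR rule names no substitute. Whether to include them is an estimand choice, to be reconciled with those sections.
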